## Funders

NIHR & HEE

This protocol describes the I4F study and provides information about procedures for entering participants. Every care was taken in its drafting, but corrections or amendments may be necessary. These will be circulated to investigators in the study. Problems relating to this study should be referred, in the first instance, to the Chief Investigator.

This study will adhere to the principles outlined in the UK Policy Framework for Health and Social Care Research. It will be conducted in compliance with the protocol, the Data Protection Act and other regulatory requirements as appropriate.

## **GLOSSARY OF ABBREVIATIONS**

## KEYWORDS

Frailty  
Video-recording  
Communication  
Patient assessment  
Care transitions  
Care continuity

## STUDY SUMMARY

TITLE	Isla for Frailty feasibility study (I4F) Acceptability, feasibility, and potential effectiveness of video-based patient records for supporting care delivery for older people with frailty.
DESIGN	Single-centre, non-randomised, mixed-methods feasibility study with embedded process evaluation
INTERVENTION	Video-based patient records (3-month pilot) alongside usual care
OBJECTIVES	
Primary objective: Determine the acceptability of using video-recordings to capture the functional abilities, support needs, and care preferences of older inpatients with frailty
 
Secondary objectives:            (a) determine the feasibility of implementing a visual medical record platform (Isla) in the acute Medicine for the Elderly setting            (b) explore the potential effectiveness of patient videos for supporting elderly inpatient care         

OUTCOME MEASURES	Acceptability of the intervention among patients & care-providers Recruitment & retention rates Intervention barriers & facilitators Video view metrics Perceived impacts on: i) inpatient assessment & clinical decision-making; ii) multi-disciplinary team communication; iii) care continuity during a hospital stay; iv) person-centred care during a hospital stay
POPULATION	Older people with frailty and their care-providers
ELIGIBILITY	Inpatients aged $\geq 65$ years with or without capacity to consent. Patients lacking capacity to consent but otherwise meeting inclusion criteria will be eligible for study participation on the condition that a 'consultee' is available to advise on the patient's likely wishes and feelings about taking part.
DURATION	17 months

## 1. INTRODUCTION

### BACKGROUND

People living with frailty represent a complex and growing challenge for health and social care providers. Around 10% of people aged over 65 years have frailty, rising to nearly 50% of those aged over 85 years, and frailty prevalence is expected to increase alongside the growth of the aging population. Older people with frailty commonly require input from multiple professionals in several organisations across primary, secondary, and social care. Professional bodies such as the British Geriatrics Society have advocated for responsible information sharing to ensure that older people with frailty are supported to age well. Yet, as patients move between different parts of the health and care service, communication between providers is frequently ineffective, assessments are duplicated, and carers are repeatedly asked to provide the same information. Poorly coordinated care is linked to avoidable complications, accelerated deconditioning, and loss of independence, as well as greater carer burden and increased costs to health and social care.

Much communication across organisational boundaries takes place through written referrals and (increasingly) through shared electronic patient records. Communication is therefore predominantly text-based, which is apposite for key clinical details (e.g. diagnosis/past medical history/medications/allergies). Comprehensive geriatric assessment and documentation standards such as those produced by the Professional Record Standards Body are known to support information exchange between professionals. However, text-based information often fails to convey the individual complexities and nuances of an older person's functional capabilities and support needs: receiving professionals may be left wondering 'Is this normal for this patient?' It is vital that health and care professionals can recognise and track subtle changes to proactively manage avoidable deconditioning and deliver individualised, person-centred care. More sophisticated modes of documentation and communication are needed to improve patient assessment and care continuity across transitions of care.

In an age of smartphones, people are increasingly telling their stories using photographs and video recordings. During the Covid-19 pandemic, remote clinical consultations using videoconferencing became routine practice. However, a clear advantage of video recording is the creation of a permanent visual record that can be reviewed by different professionals involved in a patient's care.

#### *Previous research*

A recent Cochrane review evidenced patient and health service benefits of using mobile technologies to enhance communication between healthcare providers across care settings (Gonçalves-Bradley et al 2020). In ten trials, a portable device was used to obtain clinical images (ultrasound scans, retinal images, photographs of skin conditions), which were then transmitted for further assessment. While there was some evidence that sharing still images between providers improved the timeliness of specialist assessment and treatment, none of the trials examined the application of video-recordings to enhance provider-provider communication.

We have conducted a systematic review to synthesis the academic literature and professional and regulatory guidance on video-recording patients for direct care purposes. Our review (manuscript in progress) identified 27 studies in which patients were videorecorded to support diagnosis, care, or treatment. Studies suggest that video recording patients for direct care purposes is acceptable to

most people – providing that the benefits to patients are clear and risks (privacy/ data protection) are properly mitigated.

## RATIONALE FOR CURRENT STUDY

Video recording could enhance the safety and quality of care transitions for older people with frailty through providing objective and richly detailed visual information about their functional capabilities, support needs, and care preferences. Making and sharing patient video recordings raises important ethical and legal considerations that would need to be addressed to enable the practical application of video for direct care purposes. There is a need to explore the acceptability, feasibility, and potential value of embedding in the electronic patient record video recordings captured during routine care, towards improving the safety and quality of care transitions for older people living with frailty.

## 2. STUDY OBJECTIVES

*Primary objective:*

[figure not shown]
Determine the **acceptability** of using video-recordings to capture the functional abilities, support needs, and preferences of older inpatients with frailty, to support clinical assessment and care delivery

*Secondary objectives:*

- (a) determine the **feasibility** of implementing a visual medical record platform (Isla) in the acute Medicine for the Elderly setting
- (b) explore the **potential effectiveness** of patient videos for supporting elderly inpatient care

Findings from this feasibility study will be used to refine our video-recording procedures and inform the design of a larger trial in which the effectiveness of patient video-recordings for improving the quality and safety of care transitions will be examined.

### 3. STUDY OVERVIEW & TIMELINES

(a) Standard Operating Procedure for video-recording and consent.

## 4. STUDY DESIGN

This protocol describes a single-centre, non-randomised, mixed-methods pilot study with embedded process evaluation. The revised UK Medical Research Council (MRC) framework for developing and evaluating complex interventions emphasises that feasibility assessment is essential to reduce key uncertainties around i) evaluation design (e.g. recruitment rate, outcomes), and ii) the intervention itself (e.g. acceptability, capacity of care team to deliver the intervention) (10). This current study will address key uncertainties relating to both the evaluation design and the visual patient record platform intervention to inform decisions around progression to a definitive trial.

## 5. STUDY SETTING

The setting for the study is an acute Medicine for the Elderly ward at St. Mary's Hospital, Imperial College Healthcare NHS Trust (ICHT).

## 6. PARTICIPANT ELIGIBILITY

We aim to recruit 95 participants, including patients (n=30), their carers (n=30), and ward staff (n=35).

### PATIENTS

We aim to recruit 30 patients during a 3-month pilot.

Inclusion Criteria:

- Admitted as an inpatient to the acute Medicine for the Elderly ward during a 3-month pilot phase of Isla's visual record platform
- Aged  $\geq 65$  years old
- Are considered to be frail or pre-frail by the direct care team
- Have capacity to consent to study participation OR lack capacity to consent on the condition that a 'personal consultee' is available to advise on the patient's likely wishes and feelings about taking part.

Exclusion criteria:

Patients who lack capacity to consent will be excluded if a personal consultee is not available to advise on the patients' likely wishes or feelings about taking part.

Reasonable attempts will be made to include patients who do not speak or understand English, by involving the patient's next-of-kin in interpreting, or by using local professional interpreting services (e.g. LanguageLine).

## CARERS

Patient-carer dyads will be recruited, where possible.

Inclusion Criteria:

- Aged  $\geq 18$  years
- Provide the patient/care-recipient with assistance in their daily activities and are unpaid for these caring activities
- Are willing to participate in an interview as part of the study

A carer may be a member of the patient's family, a friend, or other person who provides the patient with unpaid care.

Exclusion Criteria:

- Carers will be excluded if the patient/care-recipient declined to participate in the study.

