## 7. PARTICIPANT ENROLMENT

### PATIENTS & CARERS

**Figure 1** summarises the procedures for patient screening and enrolment. Screening and enrolment of patients and carers into the study will take place during a 3-month pilot phase of Isla's visual record platform on the Medicine for the Elderly ward. Screening and enrolment outcomes will be documented on the **screening/ enrolment log**. Potential participants (patients and carers) will be screened for eligibility by the patient's direct care team. Patients and their carers will be approached initially by members of the patient's direct care team; a team member will explain the purpose of the study and will provide a **patient and carer participant information sheets**.

Figure 1: patient screening and enrolment procedures

(a)If the patient gives any indication (whether verbal or non-verbal) that they do not wish to participate, they will not be enrolled - even if the personal consultee believes that the patient would have agreed to participate.

The first approach will take place following admission to Medicine for the Elderly ward when the patient is clinically stable. The direct care team will check whether the carer is happy to be contacted by the researcher, either by email or telephone, and will take the carer's contact details. The direct care team will flag all potential participants (patients and carers) to the researcher (an Imperial College Research Associate who holds a Licence to Attend with ICHT).

At least 24 hours after the first approach by the direct care team, the researcher will visit the patient on the ward to confirm study eligibility and to complete enrolment procedures. The researcher will approach the patient and ask them if they have any questions about the study and whether might be interested in participating. The researcher will offer to discuss the study with the patient, either at that time or another date/ time during the admission, until the patient is satisfied that all his/her questions have been answered fully. The participant information sheet contains visual aids to support the patient's understanding of what will happen to them during the study; the researcher will refer to these as needed. The researcher will offer the patient and the carer additional time to consider whether to participate.

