### ***Enrolment of carers***

Patients' family members/ informal carers will be invited to participate as interviewees. The patient will be asked to identify a family member/ informal carer (unpaid) who provides the patient with assistance in their daily activities. If the patient's family member/ carer is available at the time the researcher visits the ward, they can be included in the discussions about the study and consent to will be sought at the same time as the patient. If the carer is not available on the ward at the time of the researcher's visit, the researcher will contact the carer by telephone. The researcher will offer to discuss the study with the family member/ carer, either at that time or another date/ time, until the family member/ carer is satisfied that all his/her questions have been answered fully. The researcher will offer the family member/ carer additional time to consider whether to participate. If the family member/ carer wishes to participate, they will be asked to provide consent, by signing a printed carer consent form or by completing the electronic carer consent form; a link to this will be sent to the carer via email or SMS.

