## 9. OUTCOME MEASURES

Primary outcome measure:

- Patient, carer and staff perspectives on the acceptability of video-based records

Secondary outcome measures:

- Recruitment and retention rates
- % of patient participants with videos linked to the electronic patient record
- Video view metrics
- Intervention barriers & facilitators
- Perceived impacts of video-based records on:
  - inpatient assessment & clinical decision-making
  - multi-disciplinary team communication
  - care continuity during a hospital stay
  - person-centred care during a hospital stay
- No. of videos raising cause for concern reported to the clinical lead

**Table 1** (see overleaf) provides a summary of outcomes, measures/ approaches for obtaining data, and analyses (qualitative and quantitative), corresponding to the primary and secondary study objectives. In line with standard feasibility study objectives, clinical outcomes are not examined at this early investigative phase of the project.

Table 1: Summary of outcomes, measures/approaches, and methods of analysis

Objective	Outcomes	Measures/data collection	Methods of analysis
Acceptability	Patient/carer acceptability	
 
- % of eligible participants declining enrolment & reasons for non-participation (screening/enrolment log)
 
- % of enrolled patients with ≥ 1 video linked to the EPR
 
- Semi-structured interview at or within 2 weeks of discharge
 
	Descriptive statistics
	Direct care team acceptability	
 
- Video evaluation questionnaire
 
- Semi-structured interview after the 3-month pilot
 
- No. of videos requested, attempted & submitted (video tracker)
 
	Descriptive statistics Framework analysis Descriptive statistics & Framework analysis Framework analysis
Feasibility	Patient enrolment	
 
-% of eligible participants who were enrolled into the study (screening/enrolment log)
 
- diversity of study sample (screening/enrolment log)
 
	Descriptive statistics
	Intervention barriers & facilitators	
 
- Semi-structured interviews with patients/carers
 
- Semi-structured interviews with direct care team
 
	Framework analysis Framework analysis

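### Willingness to be interviewed is a carer inclusion criterion, so if carers are counted in Table 1's decline rate, refusals classed as ineligible drop out and the rate can only be too low

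*Protocol*

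**What the plan says.** **Eligibility.** Section 6 (Carers) sets three inclusion criteria: an age of at least 18, giving the patient unpaid help with daily activities, and "Are willing to participate in an interview as part of the study". A carer is excluded if the patient declined. The patient and ward-team criteria in section 6 contain no willingness condition.

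**What carers do.** Section 7 (Enrolment of carers) says that "informal carers will be invited to participate as interviewees". No other carer activity is described. The researcher discusses the study, offers more time, and seeks consent from carers who wish to take part.

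**The measure.** In section 9, Table 1, the patient/carer acceptability row includes the percentage "of eligible participants declining enrolment", together with "reasons for non-participation (screening/enrolment log"). In the feasibility part of the table, under the outcome for patient enrolment, stands the percentage "of eligible participants who were enrolled into the study".

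**Screening and the log.** Section 7 (Patients & Carers) speaks of screening and enrolling both groups. The next sentence begins "Screening and enrolment outcomes will be documented on the" and names the screening/enrolment log. It then says "Potential participants (patients and carers) will be screened for eligibility", and for the first approach, "The direct care team will check whether the carer is happy to be contacted by the researcher". Section 10 describes the same log as holding the eligibility and enrolment status of the patients screened, with reasons for non-enrolment.

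**The concern.** A decline rate is informative only if people who decline stay in its denominator. For carers, refusing the interview is the same act as refusing the study. Once willingness is part of eligibility, a carer who refuses can be recorded as not eligible and so is missing from a percentage taken among the eligible. The criterion repeats the consent step inside the eligibility step, and the measure depends on keeping the two apart.

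Acceptability is the primary objective, and section 4 names recruitment rate among the uncertainties to be resolved before a definitive trial. A carer decline rate that is low because of how refusals are classified could be read as evidence that carers readily take part.

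**Working it through.** The protocol gives no carer refusal rate and no target for the decline rate, so there is no stated figure to reproduce. The check has two parts.

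**1. Are carers in the measure?**
- For: the Table 1 row is labelled for patients and carers; it says participants, a term that section 6 uses to include 30 carers; and in section 7 the sentence on logging directly follows the one on screening and enrolling patients and carers.
- Against: section 10 describes the log as covering patients; the companion enrolment percentage sits under patient enrolment; and the row label could be explained by the interviews listed in the same row.

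The text leans towards counting carers but does not settle it. If only patients are counted, the bias does not arise, because patients have no willingness criterion.

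**2. If carers are counted, what happens to the rate?** Let
- N = carers who meet the age and unpaid-care criteria and whose patient has not declined;
- r = true share of these who refuse (assumed, r < 1);
- s = share of refusals classed as unwilling and therefore ineligible (assumed).

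Then:
- refusals: rN
- refusals removed as ineligible: rsN
- refusals still counted: r(1 − s)N
- carers still counted as eligible: N − rsN = (1 − rs)N
- reported decline rate = r(1 − s) / (1 − rs)
- shortfall = r − r(1 − s)/(1 − rs) = rs(1 − r)/(1 − rs), which is never negative

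The direction is therefore fixed for any r and s. Reported rates under assumed values:

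| True refusal r | s = 0 | s = 0.5 | s = 0.75 | s = 1 |
|---|---|---|---|---|
| 10% | 10% | 5.3% | 2.7% | 0% |
| 20% | 20% | 11.1% | 5.9% | 0% |
| 33.3% | 33.3% | 20.0% | 11.1% | 0% |
| 50% | 50% | 33.3% | 20.0% | 0% |

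Example: r = 0.20 and s = 0.5 give 0.20 × 0.5 / (1 − 0.10) = 0.10/0.90 = 11.1%.

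In counts, using the target of 30 enrolled carers and an assumed r of 50%: 30/0.5 = 60 carers are approached and 30 refuse. If half of the refusals (15) are classed as ineligible, the reported rate is 15/(60 − 15) = 15/45 = 33.3%. If all 30 are, it is 0/30 = 0%.

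Pooling with patients would hide the effect without removing it. With 30 enrolled in each group and a true refusal rate of 50% in both, the pooled rate should be (30 + 30)/(60 + 60) = 50%. With all carer refusals classed as ineligible it becomes 30/(60 + 30) = 33.3%.

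**The case against.** The strongest reply is that the described workflow need not produce any misclassification. At the first approach the carer is asked only for permission to be contacted, which is not the same as willingness to be interviewed. Willingness is decided later, after discussion and time to consider, when consent is sought. If staff work this way and record every refusal as a decline at consent, s = 0 and the rate is unbiased. This stands: nothing in the protocol shows that s exceeds 0. It also shows that the bullet serves no purpose, since consent already does its work, and it leaves staff free to apply the criterion as written.

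A second reply is that the log may cover patients only. That is possible, and the point is conditional for that reason. On that reading, though, a row labelled for patients and carers has no carer decline data, and sections 7 and 10 still need to agree.

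A reader might also infer that carers' reasons for refusing would be lost. The documents do not support this. Section 10 has the log record reasons for non-enrolment generally, not only among eligible decliners, and Table 1 lists reasons for non-participation. If carers are logged at all, the reasons are captured and the true refusal rate could probably be rebuilt from them.

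Finally, little rests on the number. Carers are not the people being filmed, so refusing a 30-minute interview says little about video records. The analysis is descriptive, and carers are recruited only where possible.

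**Conclusion.** The point holds as a conditional, minor flaw. If carers are counted in the decline percentage, making willingness an eligibility criterion means that the carer rate cannot exceed the true refusal rate. Only the direction is established. The size depends on two quantities that the protocol does not give: the true refusal rate and the share of refusals classed as ineligible. The tabulated values are illustrations, not estimates.

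A reader might conclude that the carer decline rate will be 0%, or that the acceptability result is undermined. Neither follows. Zero arises only if the criterion is applied literally to every refusal, and section 7 clearly allows a carer to decline after discussion. The flaw is confined to one supporting descriptive measure. The patient decline rate, the carer interviews and the other acceptability measures are unaffected, and the protocol states no threshold that uses this rate.

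**What to change.** 1. In section 6 (Carers), delete the willingness criterion and leave willingness to the consent step in section 7.
2. In Table 1, report the carer decline rate separately from the patient rate. Its denominator should be identified carers aged 18 or over who give unpaid care to a patient who has not declined. Refusals at first approach should count as declines.
3. Make section 10 agree with section 7 on whether the screening/enrolment log covers carers. If it does, record each carer's enrolment status and reason for declining.
4. If the measure is meant for patients only, say so in Table 1; step 2 is then not needed.

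The cost is one deleted bullet, one split table row, one sentence in section 10 and one carer column in the log. The only drawback is that the reported carer decline rate may look less favourable.
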